### III. Participant Withdrawal

Participants are free to withdraw at any point from the study. If a participant indicates their desire to withdraw from the study, we will not collect any further interview data from the participant. Any data collected previously from a participant who withdraws from the study will be destroyed [removed from the SPSS (quantitative) and NVivo (qualitative) databases and not included in analyses].

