**Aim 3:** Aim 3 involves an intervention and 4 individual interviews with each participant. The Immigrant Well-being Project (IWP) Intervention Model is a 6-month intervention with two main components: 1) Learning Circles. Learning Circles (LCs) occur once per week for six months (total of 24 LCs). Each meeting is two hours and includes immigrants and undergraduate paraprofessionals. LCs have two parts: cultural exchange and one-on-one learning. Cultural exchange occurs for the first hour and is facilitated together by one undergrad and one immigrant who choose the topic. To enable all participants to share in the discussion, interpreters are present. Cultural exchange provides a forum for immigrants and undergrads to learn from each other, share ideas, develop plans for collective action, and realize the important contributions they are capable of making. The second component of the LCs is one-on-one learning. For the last hour, immigrants and undergrads work in pairs. During one-on-one time, immigrants direct their own learning (e.g. English, job applications). 2) Advocacy. Advocacy begins after the first two weeks of LCs. For the remaining 5½ months of *IWP*, undergrads spend an additional 4-6 hours each week (outside of the LCs) with their immigrant partner(s) to engage in advocacy together around any issues the immigrant(s) would like to address. They follow a 4-phase process (assessment, implementation, monitoring, and secondary implementation) for each unmet need or goal. Undergrads also work to transfer advocacy skills to their partner, through shared engagement in advocacy, modeling, and role plays. The *IWP* employs a holistic approach that integrates advocacy and learning to address multiple needs of immigrants (i.e., English proficiency, access to resources, understanding of their environment, social support, valued social roles). However, rather than emphasizing only what immigrants need to learn to survive in the U.S., the *IWP* focuses on

**mutual learning**, through which immigrants both learn from and teach people born in the U.S.

Quantitative interview procedure. Each participant will complete 4 quantitative interviews: pre, mid (~3 months after pre), post (~6 months after pre), and follow-up (14 months after pre). The 1-1½ hour

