### **II. Data Analysis/Statistical Considerations**

Quantitative data analysis. All raw data will be examined to verify quality and identify potential outliers and distributional issues. Psychometric properties of existing scales will be verified, and psychometric analyses will be conducted on modified measures. To reduce Type I errors, data reduction (e.g., second-order confirmatory factor analysis) will be used, where feasible, to guide the combination of individual scales and variables into meaningful constructs. Significant findings on composite constructs will be followed up with parallel analyses on component variables. Additional

analyses will identify characteristics of individuals who drop out or receive lower dosage. Covariates of attrition will be used to estimate complier average causal effects. Although missing data will be minimized through use of incentives, culturally sensitive assessment, and proactive retention strategies, it is a potential problem in longitudinal research. Pattern mixture modeling will be used to determine whether missing data affect study conclusions or are “ignorable” (i.e., conditionally missing at random). Missing data determined to be ignorable will be estimated using expectation maximization and multiple imputation procedures appropriate for longitudinal data. Sensitivity analysis will be used to examine the possible impact on study conclusions involving any missing data found to be non-ignorable.

***Hypothesis 3.2*** *Participants in IWP will show lower psychological distress over time and*

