***Hypothesis 3.3*** *IWP participants’ protective factors (access to resources, English proficiency, environmental mastery, social support) will increase significantly over time.* Growth curve modeling will be implemented using hierarchical linear modeling (HLM). Analyses will proceed sequentially beginning with baseline ‘intercept-only’ models, then testing fully parameterized model (see Goodkind, et al., 2012 for detailed description of analytic method). If this iterative process identifies that the best fitting model includes significant random effects corresponding to the significant fixed effects (i.e., that there is significant variability in intercepts and/or slopes), we will attempt to model it using level-2 predictors. Level-2 predictors to be tested as potential moderators will include sex, age, length of time in the U.S., and intervention hours, which will allow us to identify relevant individual difference variables (e.g., age) that may predict response to the intervention and to test whether intervention dosage predicts differential change (a finding that would strengthen the inference of treatment effects). Calculating effect sizes for multilevel models is complex; because our focus will be the effect of the intervention over time, we will examine the percentage of variance explained (PVE) by the addition of time to each model by comparing the PVE of the best fit Level 1 model to the Level 1 intercept-only model.

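### Destroying the earlier interview data of participants who state a wish to withdraw leaves the growth models and the promised dropout and missing-data analyses with no scores for those people

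*Combined protocol and SAP*

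**What the plan says.** Under STUDY DATA, section III (Participant Withdrawal), once a participant indicates a wish to withdraw, no more interview data are collected. The section continues: "Any data collected previously from a participant who withdraws from the study will be destroyed". A bracket spells this out: the data are "removed from the SPSS (quantitative) and NVivo (qualitative) databases and not included in analyses". No other section makes an exception.

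STUDY DATA, section II (Data Analysis/Statistical Considerations) promises work that draws on what was observed before a person left:

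- a profile of leavers: "analyses will identify characteristics of individuals who drop out or receive lower dosage";
- use of that profile: "Covariates of attrition will be used to estimate complier average causal effects";
- pattern-mixture modeling, which "will be used to determine whether missing data affect study conclusions";
- "Sensitivity analysis will be used to examine the possible impact on study conclusions involving any missing data found to be non-ignorable".

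The same section tests Hypotheses 3.2 and 3.3 with growth curves fitted by hierarchical linear modeling. STUDY DESIGN, section V places the interviews at baseline and at about 3, 6 and 14 months. Section II of STUDY DESIGN enrols 90 participants in Aim 3, all of whom receive the intervention.

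**The concern.** A growth model can use a partial record: someone with pre and mid scores who then leaves still informs the slope. Pattern-mixture and sensitivity analyses likewise start from the scores observed before dropout. A person whose record has been destroyed is not a case with missing values. That person is absent from the file, and these methods cannot detect or adjust for the absence.

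Hypothesis 3.2 is a decrease in distress within one group. There is no comparison arm in which similar deletions might partly offset the effect, so the result describes change among people whose records remain. A link between distress and withdrawal is plausible, because the Potential Risks section accepts that the mental health and trauma questions may upset participants. If withdrawal is linked to change in distress, deletion shifts the estimate, and the observed scores that would have corrected it are gone for good.

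**Working it through.** **Scope.** The rule is triggered by a stated wish to withdraw. Missed interviews, skipped questions, poor attendance and silent loss to follow-up do not trigger it. For those people earlier data stay and every planned analysis can run. Adverse-event reporting is also unaffected.

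**No plan figure to reproduce.** The documents give no withdrawal rate, SD, effect size or power for the 90 participants. What follows is illustrative.

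**Inputs from the documents.** N = 90; one group; interviews at 0, 3, 6 and 14 months; growth model over all four.

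**Assumed inputs.**
- Score = b0 + b1·t + e, with t = months/6 and true mean slope 0.
- Intercept variance 0.7 and residual variance 0.3, so the baseline SD is sqrt(0.7 + 0.3) = 1.00.
- Slope variance 0.1 or 0.4 per (6 months)², with no intercept-slope covariance.
- Worse means a pre-to-mid rise of at least 0.5.
- Withdrawal after mid has probability w = 0.10, 0.20 or 0.40 if worse, and 0.05 otherwise.

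**Outcome SD at 14 months.**
- Slope variance 0.1: sqrt(1 + 0.1 × (14/6)²) = 1.24.
- Slope variance 0.4: sqrt(1 + 0.4 × (14/6)²) = 1.78. This is a large spread, so treat it as the high case.

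**Expected deletions.** The SD of the pre-to-mid change is sqrt(0.25 × slope variance + 2 × 0.3).
- Slope variance 0.1: SD 0.791; P(worse) = 1 - Φ(0.5/0.791) = 0.264, or 23.7 of 90. Deletions = 23.7w + 66.3 × 0.05 = 5.7, 8.1 or 12.8.
- Slope variance 0.4: SD 0.837; P(worse) = 1 - Φ(0.5/0.837) = 0.275, or 24.8 of 90. Deletions = 24.8w + 65.2 × 0.05 = 5.7, 8.2 or 13.2.

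**Simulated slope.** Generalised least squares with known covariance, 20,000 trials per cell; a false decrease is z < -1.96.

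| Slope variance | w | Bias with deletion (SD per 6 months) | False decreases | Bias if scores kept |
|---|---|---|---|---|
| 0.1 | 0.10 | -0.002 | 2.8% | about 0 |
| 0.1 | 0.20 | -0.007 | 3.5% | about 0 |
| 0.1 | 0.40 | -0.017 | 5.3% | about 0 |
| 0.4 | 0.10 | -0.006 | 3.1% | about 0 |
| 0.4 | 0.20 | -0.017 | 4.0% | about 0 |
| 0.4 | 0.40 | -0.041 | 7.4% | about 0 |

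Repeat runs gave the same slopes to within 0.001; the 7.4% came out between 7.0% and 7.4%. With scores kept, false decreases stayed at 2.3% to 2.7%. With w = 0.05 in both groups there was no bias.

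**Estimated variances.** A smaller REML check (slope variance 0.4, 1,000 trials per cell, Monte Carlo SE 0.6 to 0.8 points) gave 4.0%, 5.2% and 7.1% with deletion against 3.2%, 3.3% and 3.7% with scores kept. The excess is 0.8, 1.9 and 3.4 points, and the first cannot be told from noise.

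**Opposite direction.** If those who improve by at least 0.5 leave instead (slope variance 0.4), the bias is about +0.005, +0.017 and +0.040, and false decreases fall to about 2.1%, 1.5% and 0.6%.

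**Range analysis.** The all-enrolled estimate moves by (deleted/90) × the assumed difference from those kept. At ±0.5 SD per 6 months:
- 6 deletions: 6/90 × 0.5 = 0.033
- 8 deletions: 8/90 × 0.5 = 0.044
- 13 deletions: 13/90 × 0.5 = 0.072

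The differences implied by the high case are the bias divided by the deleted fraction: 0.0056/(5.7/90) = 0.09, 0.0167/(8.2/90) = 0.18 and 0.0409/(13.2/90) = 0.28. A range of ±0.5 covers all three.

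**The case against.** Erasure on withdrawal fits a protocol built to protect people who may lack legal status: signatures are waived, identifiable data are minimised, and recordings and the master list are later destroyed. The withdrawal section does not give this reason, but it is a defensible ethical choice, and any fix must leave deletion available. That stands. It does not remove the conflict with the planned analyses, and default deletion goes further than a participant may want.

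The size objection also stands. The effect is small unless withdrawal is strongly tied to distress, and no withdrawal rate is given.

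Four stronger readings are tempting, and the documents do not support them:

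- **The dropout and missing-data analyses are void.** They fail only for people who state a wish to withdraw.
- **The rule favours the intervention.** The direction depends on who leaves, which the documents do not say.
- **There will be no trace of withdrawals.** The Unanticipated Problems/Adverse Events section provides for monthly review of recruitment and retention data, which are not described as part of the purged databases. That review could yield a count, though no tally by interview is promised and a count holds no scores.
- **The false-positive rate could reach 13% or 25%.** Such figures arise for pre-to-post change at 20% or 30% withdrawal, under different assumptions and strong dependence on worsening. The same inputs through the four-interview slope, which is what the plan specifies, gave about 5.8% and 7.9%.

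**Conclusion.** The point holds within its limits. The rule is explicit and has no exception. For participants who formally withdraw, it defeats analyses that the plan itself promises. If withdrawal depends on change in distress, the single-group Hypothesis 3.2 estimate is biased in a direction that the documents do not settle; if it does not, only sample size is lost.

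Under the assumed inputs, the bias when people who worsen leave runs from -0.002 to -0.017 SD per 6 months with the smaller slope variance, and from -0.006 to -0.041 with the larger. False decreases run from about 3% to 5% and from about 3% to 7%. The upper ends need 40% withdrawal among those who worsen, eight times the rate in others. This is a modest risk, worth removing because the remedy is cheap and destroyed scores cannot be recovered. Confidence is high on the text and medium on the consequence.

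**What to change.** 1. Reword the Participant Withdrawal section and the matching consent language. Withdrawal ends contact and further data collection. The participant is then asked whether coded data already collected may stay in the analysis or should be deleted. Carry out that choice first, then delete the participant's line in the master list.
2. As part of the existing monthly retention review, record withdrawals and requested deletions by interview (after pre, mid or post), without identifiers.
3. If any deletions occur, repeat the Hypothesis 3.2 analysis over a two-sided range of assumed change for the deleted participants, for example from 0.5 SD worse to 0.5 SD better per 6 months, and report whether the conclusion changes.

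Cost: an IRB amendment, one question at exit, a short tally and one extra analysis if needed. No visits or measures are added. Some participants may still choose deletion, and that right is kept. Anyone who consented under the existing rule keeps it unless they agree to the change.

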### PRIOR APPROVALS/REVIEWED AT OTHER IRBS

---

N/A

